5.4.2. Safety Endpoints

Safety endpoints consist of the incidences of TEAEs, SAEs and discontinuations due to adverse events (AEs), vital signs (blood pressure [BP], pulse, and body temperature), weight, suicidal ideation and behaviors assessed by solicited questioning using the C-SSRS, ECGs, laboratory measures (chemistry, hematology, and urinalysis).

5.4.3. Immunogenicity Endpoints

Immunogenicity endpoints consist of the incidences of antibodies to galcanezumab (ADA). An additional endpoint is the incidence of NAb present in those trial participants with ADA.

CCI

CCI

CCI

5.5. Statistical Analyses

The protocol for this study was approved on 18 December 2014. Protocol amendment (a) for this study was approved on 27 March 2015. Protocol amendment (b) for this study was approved on 22 December 2015. Protocol amendment (c) for this study was approved on

10 February 2017. The SAP Version 4 supersedes the statistical plans described in the protocol and previous versions of the SAP.

5.5.1. General Considerations

General aspects of statistical analyses are described below.

Unless otherwise specified, efficacy analyses will be conducted on an **intent-to-treat (ITT) population**, which include all patients who are randomized and receive at least one dose of study drug. Patients in the ITT population will be analyzed according to the treatment group that they were randomized to. Safety analyses for SP III will be conducted on the **safety population** which also includes all patients who are randomized and receive at least one dose of study drug. However, patients will be analyzed by actual study treatment received most often (modal treatment) during the double-blind treatment phase. Modal treatment will be the same as randomized treatment except in some cases of incorrect treatment administration. When mean change from baseline is assessed, the patient will be included in the analysis only if he/she has a baseline and a post-baseline measurement.

The additional analyses populations are described in [Table CGAM.5.2](#).

Safety analyses (Section [5.5.9](#)) and analyses for exposure will be conducted based on the modal treatment group patients have received (placebo or GMB300mg) during the double-blind treatment phase. For determining modal treatment, if there are 2 modes, then the modal treatment group will be GMB300mg.

Table CGAM.5.2. Study Phase, Analysis Population and Corresponding Treatment Groups

Study Phase (SP)	Analysis Population	Population Definition	Treatment Groups
SP III	ITT Population	All patients who are randomized and receive at least one dose of study drug	SP III treatment (based on randomization): Placebo, Galcanezumab 300mg (GMB300mg)
SP III and first 4 weeks of SP IV combined ^a			
SP III	Safety Population	All patients who are randomized and receive at least one dose of study drug	SP III treatment (based on modal treatment arm): Placebo, GMB300mg
SP IV	Open-label population	All patients who entered the open-label extension phase (SP IV) as indicated by receiving any injections in any open-label extension visit	SP III/IV treatment: Placebo-GMB300mg, GMB300mg-GMB300mg
SP III/IV Combined (GMB-treated time)	GMB-treated population	All patients who have exposure to Galcanezumab: 1) patients who received GMB300mg during SP III;	SP III/IV treatment: GMB300mg

Study Phase (SP)	Analysis Population	Population Definition	Treatment Groups
SP III/IV/V Combined (GMB-treated time + post treatment time)		2) patients who received placebo during SP III and entered the open-label phase with at least one galcanezumab injection.	

Abbreviations: ePRO = electronic patient reported outcome; GMB = galcanezumab; SP = study phase.

a Analyses in SP III and first 4 weeks of SP IV combined, will be conducted for ePRO data only.

Treatment effects will be evaluated based on a 2-sided significance level of 0.05 for all the other efficacy and safety analyses. Ninety-five percent (95%) CI for the difference in least-square means (LSMeans) between treatment groups will be presented. Adjustments for multiple comparisons for the analyses corresponding to the primary and gated secondary objectives are described in the sections on the primary and secondary efficacy analyses below. There will be no adjustments for multiplicity for analyses of other data.

A repeated measures analysis refers to a restricted maximum likelihood (REML)-based, mixed-effects repeated measures (MMRM) analysis using all the longitudinal observations at each postbaseline visit/week.

Categorical comparisons between treatment groups for safety measures will be performed using Fisher's exact tests, where appropriate.

Any change to the data analysis methods described in the protocol will require an amendment ONLY if it changes a principal feature of the protocol. Any other change to the data analysis methods described in the protocol, and the justification for making the changes, will be described in the SAP and/or in the clinical study report.

Additional exploratory analyses of the data will be conducted as deemed appropriate.

Statistical analysis of this study will be the responsibility of Eli Lilly and Company (Lilly) or designee. SAS®software will be used to perform most or all statistical analyses.

5.5.1.1. Adjustments for Covariates

The repeated measures models will include the fixed, categorical effects of treatment, gender, verapamil use, pooled investigative site, visit/week, and treatment-by-visit/week interaction, as well as the continuous, fixed covariates of baseline value. Rules for pooling of investigative sites are described in Section 5.5.1.3. Note: in repeated measures analysis, visit will be used for measures collected at visit interval, while week will be used for all the ePRO data.

The categorical, pseudo-likelihood-based repeated measures models for the visitwise/weekwise binary outcomes of response will include the fixed, categorical effects of treatment, gender, verapamil use, visit/week, and treatment-by-visit/week interaction, as well as the continuous, fixed covariate of baseline value. Pooled investigative site was not included in the model in order to increase the likelihood of convergence.

With the exception of efficacy analyses on cluster headache frequency or categorical analysis of response rate (such as 50% response rate) derived from cluster headache frequency where the continuous value of baseline weekly cluster headache frequency will be used as covariate, all other efficacy analyses will include baseline average daily cluster headache attack frequency category (≤ 4 vs > 4) as a covariate in the MMRM and GLIMMIX model.

5.5.1.2. Handling of Dropouts or Missing Data

Repeated measures analyses will be used as the statistical approach for handling missing data. The model parameters are simultaneously estimated using restricted likelihood estimation incorporating all of the observed data. Estimates have been shown to be unbiased when the missing data are missing at random and when there is ignorable non-random missing data (Mallinckrodt et al. 2008). Missing at random (MAR) assumption will be evaluated using sensitivity analyses as defined in Section 5.5.11.

Approaches for handling missing data for derivation of cluster headache attacks derived from ePRO per 14-day interval

In Study CGAM, for primary measure of cluster headache attacks, the daily data for each patient (including last 14 days in the eligibility report [pre-randomization diary phase], 12 weeks of daily data during double-blind treatment phase and 4 weeks of daily data during open-label extension phase) will be converted into 9 roughly 14-calendar day intervals: the baseline 14-day interval(baseline), Weeks 1/2, 3/4, 5/6, 7/8, 9/10, 11/12, 13/14, and 15/16. Each day, the patient may have zero, one, or multiple cluster headache attacks. For each biweekly interval, the following missing data imputation method will be used:

- 1) If there are ≤ 7 days with non-missing answer to cluster headache attack frequency in the biweekly interval; or 2) the diary compliance rate is $\leq 50\%$, then the biweekly interval will be considered missing;
- Otherwise, 1) if there are ≥ 8 days with non-missing answer to cluster headache attack frequency in the biweekly interval; and 2) the diary compliance rate is $> 50\%$, then the average number of cluster headache attacks across the non-missing days will be used to impute the missing days.

For detailed example about missing data imputation, please see Section 5.4.1.2.

Then the change from baseline to Weeks 1/2, 3/4, 5/6, 7/8, 9/10, and 11/12 will be derived.

The same approach will also be applied to secondary and exploratory efficacy measures that derived from ePRO data.

5.5.1.3. Multicenter Studies

At the time of IA1 as well as at the time of IA2 (final analyses of primary efficacy measures) if sample size is not increased, the following investigative site pooling method will be used:

All investigative sites with fewer than 2 randomized patients per each treatment group with non-missing cluster headache attacks during baseline interval and at least one post-baseline value will

be pooled together within each country and considered a single site for analyses. If this results in a pooled site still having fewer than 2 randomized patients per each treatment group, the pooled site will also be pooled with the next smallest site in that country, determined to be the site with the smallest number of randomized patients, or if more than one site meets that criterion, the smallest site with the lowest investigator number. If this results in a pooled site still having fewer than 2 patients randomized to each treatment arm, these sites will be pooled together with the next smallest site in the geographic region. Two geographic regions are defined including US and Canada combined, as well as Europe. If this still results in a site having fewer than 2 patients randomized to each treatment, then these sites will be pooled together with the next smallest site in the whole study.

However, at the time of IA2 (final analyses of primary efficacy measures) if sample size is increased, the following investigative site pooling method will be used:

The same pooled investigative sites as used for IA1 will be used for IA2. In other words, the sites that had been pooled in IA1 will be kept as a pooled site regardless of the number of patients in post-interim 1 data. In addition, for data at post-interim 1, if a new site added after IA1 has fewer than 2 randomized patients per each treatment group with non-missing cluster headache attacks during baseline interval and at least one post-baseline value for the post-interim 1 data, the site will also be pooled with the next smallest site in that country, determined to be the site with the smallest number of randomized patients, or if more than one site meets that criterion, the smallest site with the lowest investigator number. If this results in a pooled site still having fewer than 2 patients randomized to each treatment arm, these sites will be pooled together with the next smallest site in the geographic region. Two geographic regions are defined including US and Canada combined, as well as Europe. If this still results in a site having fewer than 2 patients randomized to each treatment, then these sites will be pooled together with the next smallest site in the whole study.

All analyses will use pooled investigative sites. The actual investigative site numbers will be included in the listings.

5.5.1.4. Multiple Comparisons/Multiplicity

The primary efficacy analysis will be the overall treatment effect of galcanezumab 300 mg every 30 days vs. placebo using a MMRM analysis, which is equivalent to the average of the MMRM-estimated weekly treatment effect over the 12-week double-blind treatment phase for change in weekly cluster headache attack frequency from baseline. The Type I error rate will be controlled at a 1-sided 0.025 level for the primary efficacy analysis.

A fixed sequential gatekeeper method will be utilized for testing secondary hypotheses to be eligible for inclusion in the proposed label. Specific details of the testing of the secondary gatekeeper objectives are provided in Section [5.5.8.2](#).

5.5.1.5. Analysis Populations

Four analysis populations including ITT population, safety population, open-label population, and GMB-treated population are defined in Section [5.5.1](#).

5.5.1.6. Baseline and Postbaseline Definition

Table CGAM.5.3 describes the rules for determining the patient population and baseline and postbaseline observations for each study phase and type of analysis. When “last of Visit x-x” is used in the table, the last nonmissing observation obtained in the visit interval will be used.

Table CGAM.5.3. Patient Population with Baseline and Postbaseline Definitions by Study Phase and Type of Analysis

Study Phase / Analysis	Patient Population	Baseline Observation	Postbaseline Observation(s)
Study Phase III (Treatment Phase)			
Continuous secondary efficacy analyses (Repeated measures)	Patients in ITT population with a baseline and at least one postbaseline observation	Visit 3	All Visits 4–9
TEAEs	Safety population	All Visits 1–3 before dosing	Visit 3 after dosing – through Visit 9 before dosing if applicable
Serious Adverse Events, Discontinuations due to Adverse Events	Safety population	NA	Visit 3 after dosing – through Visit 9 before dosing if applicable
C-SSRS categorical analyses	Patients in safety population with a baseline and at least one postbaseline C-SSRS assessment	Recent History: All Visits 1–3 excluding lifetime ^a All Prior History: Visits 1–3 including lifetime ^a	All Visits 3.01–9
Treatment-emergent abnormal laboratory values	Patients in safety population with normal laboratory values at all nonmissing baseline visits (with respect to direction being analyzed) and who have at least one postbaseline observation	All Visits 1–3	All Visits 3.01–9
Treatment-emergent immunogenicity	Patients in safety population who are evaluable for TE ADA	Visit 3	All Visits 3.01–9
Treatment-emergent changes in vital signs and weight, ECG parameters	Patients in safety population with a baseline and at least one postbaseline observation	Last non-missing value from Visits 1–3 for BP, pulse and ECG All Visits 1–3 for weight and temperature	All Visits 3.01–9
Continuous safety analysis of vital signs, weight, laboratory and ECG parameters (box-whisker plot)	Safety population	Last non-missing value from Visits 1–3	Visits 4–9

Patient Population with Baseline and Postbaseline Definitions by Study Phase and Type of Analysis

Study Phase / Analysis	Patient Population	Baseline Observation	Postbaseline Observation(s)
Study Phase III and IV combined (Double-blinded and open-label extension phase combined)			
Efficacy analyses (measures derived from e-PRO)	Patients in ITT population with a baseline and at least one postbaseline observation	Visit 3	All Visits 4-11
TEAEs	GMB-treated population	Visits 1-3 before double-blind phase dosing for patients treated with GMB during SP III; Visits 1-9 before open-label phase dosing for patients treated with placebo during SP III.	All visits on or after first dosing of GMB up to Visit 22: Visit 3 after dosing to Visit 22 for GMB-treated patients during SP III; Visit 9 after dosing to Visit 22 for placebo treated patients during SP III.
SAEs, Discontinuations due to AEs	GMB-treated population	NA	All visits on or after first dosing of GMB up to Visit 22: Visit 3 after dosing to Visit 22 for GMB-treated patients during SP III; Visit 9 after dosing to Visit 22 for placebo treated patients during SP III.

Patient Population with Baseline and Postbaseline Definitions by Study Phase and Type of Analysis

Study Phase / Analysis	Patient Population	Baseline Observation	Postbaseline Observation(s)
C-SSRS categorical analyses	Patients in GMB-treated population with a baseline and at least one postbaseline C-SSRS assessment	Recent History: All Visits 1-3 excluding lifetime ^a for patients treated with GMB during SP III; Visits 1-9 for patients treated with placebo during SP III. All Prior History: Visits 1-3 including lifetime ^a for patients treated with GMB during SP III; Visits 1-9 for patients treated with placebo during SP III.	All visits after first dosing of GMB up to Visit 22: Visit 3.01-22 for GMB-treated patients during SP III; Visits 9.01-22 for placebo treated patients during SP III.
Treatment-emergent abnormal laboratory values	Patients in GMB-treated population with normal laboratory values at all nonmissing baseline visits (with respect to direction being analyzed) and who have at least one postbaseline observation	Visits 1-3 before double-blind phase dosing for patients treated with GMB during SP III; Visits 1-9 before open-label phase dosing for patients treated with placebo during SP III.	All visits after first dosing of GMB up to Visit 22: Visits 3.01- 22 for GMB-treated patients during SP III; Visits 9.01-22 for placebo treated patients during SP III.

Patient Population with Baseline and Postbaseline Definitions by Study Phase and Type of Analysis

Study Phase / Analysis	Patient Population	Baseline Observation	Postbaseline Observation(s)
Treatment-emergent changes in vital signs and weight, ECG parameters	Patients in GMB-treated population with a baseline and at least one postbaseline observation	
For patients treated with GMB during SP III: Last non-missing value from Visits 1-3 for BP, pulse and ECG;
 
All Visits 1-3 for weight and temperature;
 
For patients treated with placebo during SP III: Last non-missing value from Visits 1-9 for BP, pulse and ECG;
 
All Visits 1-9 for weight and temperature.
	All visits after first dosing of GMB up to Visit 22: Visits 3.01-22 for GMB-treated patients during SP III; Visits 9.01-22 for placebo treated patients during SP III.
Treatment-emergent immunogenicity	Patients in GMB-treated population who are evaluable for TE ADA	Visit 3	All visits after first dosing of GMB up to Visit 22: All Visits 3.01-22 for GMB-treated patients during SP III; All Visits 9.01-22 for placebo treated patients during SP III.

Patient Population with Baseline and Postbaseline Definitions by Study Phase and Type of Analysis

Study Phase / Analysis	Patient Population	Baseline Observation	Postbaseline Observation(s)
Study Phase IV (Open-label Extension Phase)			
Efficacy analyses (PGI-I)	Open-label population		V16 and V22
Study Phase III, IV and V			
TEAEs	GMB-treated population	Visits 1-3 before double-blind phase dosing for patients treated with GMB during SP III; Visits 1-9 before open-label phase dosing for patients treated with placebo during SP III.	All visits on or after first dosing of GMB up to Visit 24: Visit 3 after dosing– Visit 24 for GMB-treated patients during SP III; Visit 9 after dosing to Visit 24 for placebo treated patients during SP III.
SAEs, Discontinuations due to AEs	GMB-treated population	NA	All visits on or after first dosing of GMB up to Visit 24: Visit 3 after dosing to Visit 24 for GMB-treated patients during SP III; Visit 9 after dosing to Visit 24 for placebo treated patients during SP III.

Patient Population with Baseline and Postbaseline Definitions by Study Phase and Type of Analysis

Study Phase / Analysis	Patient Population	Baseline Observation	Postbaseline Observation(s)
C-SSRS categorical analyses	
Patients in GMB-treated population with a baseline and at least one postbaseline C-SSRS assessment
	
Recent History: All Visits 1-3 excluding lifetime^a for patients treated with GMB during SP III; Visits 1-9 for patients treated with placebo during SP III.
 
All Prior History: Visits 1-3 including lifetime^a for patients treated with GMB during SP III; Visits 1-9 for patients treated with placebo during SP III.
	
All visits after first dosing of GMB up to Visit 24: Visits 3.01-24 for GMB-treated patients during SP III; Visits 9.01- 24 for placebo treated patients during SP III.

Treatment-emergent abnormal laboratory values	
Patients in GMB-treated population with normal laboratory values at all nonmissing baseline visits (with respect to direction being analyzed) and who have at least one postbaseline observation
	
Visits 1-3 before double-blind phase dosing for patients treated with GMB during SP III; Visits 1-9 before open-label phase dosing for patients treated with placebo during SP III.
	
All visits after first dosing of GMB up to V24: Visits 3.01-24 for GMB-treated patients during SP III; Visits 9.01-24 for placebo treated patients during SP III.

Patient Population with Baseline and Postbaseline Definitions by Study Phase and Type of Analysis

Study Phase / Analysis	Patient Population	Baseline Observation	Postbaseline Observation(s)
Treatment-emergent changes in vital signs and weight, ECG parameters	Patients in GMB-treated population with a baseline and at least one postbaseline observation	For patients treated with GMB during SP III: Last non-missing value from Visits 1-3 for BP, pulse and ECG; All Visits 1-3 for weight and temperature; For patients treated with placebo during SP III: Last non-missing value from Visits 1-9 for BP, pulse and ECG; All Visits 1-9 for weight and temperature.	All visits after first dosing of GMB up to V24; Visits 3.01-24 for GMB-treated patients during SP III; Visits 9.01-24 for placebo treated patients during SP III.
Treatment-emergent immunogenicity	GMB-treated population with post-treatment ADA assessment who are evaluable for TE ADA.	Visit 3	All visits after first dosing of GMB up to Visit 24; All Visits 3.01-24 for GMB-treated patients during SP III; All Visits 9.01-24 for placebo treated patients during SP III.

Abbreviations: ADA = anti-drug antibody; AE = adverse event; BP = blood pressure; C-SSRS = Columbia Suicide Severity Rating Scale; ECG = electrocardiogram; ePRO = electronic patient-reported outcome; GMB = galcanezumab; ITT = intent-to-treat; NA = not applicable; SAE = serious adverse event; TE ADA = treatment emergent anti-drug antibody; TEAE = treatment-emergent adverse event.

Note: Visit 3.01 indicates the first unscheduled visit occurring after Visit 3 and prior to Visit 4. Visit 9.01 indicates the first unscheduled visit occurring after Visit 9 and prior to Visit 10.

a Lifetime is captured in the C-SSRS Visit 1 case report form.

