7.1. Summary of Study Design

Study CGAM is a Phase 3 multi-center, outpatient, randomized, double-blind, placebo-controlled study of LY2951742 300 mg for the prevention of chronic cluster headache. The study has 5 study phases (SP):

- SP I (screening/washout phase)
- SP II (pre-randomization diary phase)
- SP III (double-blind treatment phase)
- SP IV (optional open-label extension phase)
- SP V (post-treatment follow-up phase)

Figure CGAM 1 illustrates the study design.

Abbreviations: ePRO = electronic patient reported outcome; SP = study phase; X = injection of investigational product.

^a ePRO diary reporting will be completed daily during SP II and SP III. “Day” will be defined on a 24- clock day.

^b Patients begin recording in their diary on a daily basis and call site to schedule Visit 2 and Visit 3.

^c Visit 2 will occur during SP II. The minimum time between Visit 2 and Visit 3 is 5 days.

^d Scheduling of this office visit, Visit 3, should take into consideration that patients must have at least 14 days to record a baseline assessment of cluster headache attack frequency prior to Visit 3.

^e Telephone visit 7 days after office visit only for assessment of spontaneously reported AEs.

Figure CGAM.1. Illustration of study design for clinical protocol I5Q-MC-CGAM.

Study Phase I is the screening/washout phase beginning at Visit 1 to the start of SP II and lasting for a minimum of 0 days to a maximum of 65 days. Patients will sign an informed consent form (ICF) at Visit 1 prior to completing study-related initial screening procedures. At Visit 1, patients will discontinue excluded medications, non-fasting laboratory samples will be collected (fasting laboratory samples are collected at visits indicated in the study schedule), and other additional baseline procedures will be performed to determine further eligibility (see Study Schedule, [Attachment 1](#)).

At Visit 1, for patients who meet initial screening criteria, an ePRO diary may be dispensed to the patient to record his or her daily cluster headache attack information and allowed use of abortive treatments (collectively referred to as ‘daily cluster headache attack information’ throughout the protocol). Visit 1 will be considered complete when the last scheduled procedure of the screening assessment for the patient is completed.

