Vital sign	X	X	X		X		X	X		Vital signs will also be taken at unscheduled office visits. Vital signs include body temperature, blood pressure, and pulse. Blood pressure and pulse will be measured in triplicate in the sitting position and should be measured prior to blood draws. Blood pressure will be assessed by utilizing a calibrated machine that will be provided to the sites.
Hematology	X		X					X		
Clinical chemistry ^a	X		X					X		Except for V1, chemistry labs require fasting (no food or drink, except water, for at least 8 hrs).
Urinalysis	X							X		
HbA1C	X							X		

Study Schedule, Protocol I5Q-MC-CGAM: SP I to SP III

Study Phase (SP)	SP I	SP II	SP III							
Description	Screening	Pre-Randomization Diary	Treatment						Comments	
Visit	1	2	3	4 (Phone visit)	5	6	7 (Phone visit)	8	9	Comments
Month						1		2	3	
Serum Pregnancy or FSH	X									Female patients only
Urine drug screen	X									
Randomization			X							
Immunogenicity			X		X	X		X	X	Immunogenicity samples must be collected prior to dose administration if the visit is a dosing visit. Samples will be taken in the event of early termination. The timing of samples will be recorded.
										CCI [REDACTED]
Plasma Storage Sample (K+/EDTA)	X	X	X		X	X		X	X	Samples must be collected prior to dose administration if the visit is a dosing visit. The timing of the samples will be recorded. These samples will be collected in an K+/EDTA container.
PK sampling					X	X		X	X	Samples must be collected prior to dose administration if the visit is a dosing visit. The timing of the samples will be recorded.
CCI [REDACTED]			C							[REDACTED]
RNA storage sample	X	X		X	X		X	X		Sample must be collected in a Tempus tube.

Study Schedule, Protocol I5Q-MC-CGAM: SP I to SP III

Study Phase (SP)	SP I	SP II	SP III							
Description	Screening	Pre-Randomization Diary	Treatment							Comments
Visit	1	2	3	4 (Phone visit)	5	6	7 (Phone visit)	8	9	Phone visits (V4 and V7) are contacts between office visits to collect any spontaneously reported AE after the first two injections of IP.
Month					1			2	3	
PGI-I					X			X	X	
C-SSRS/SHSF, SHFU	X	X	X		X			X	X	Should also be completed at unscheduled office visits.
Recording of AEs	X	X	X	X	X	X	X	X	X	
Review Diary data			X	X		X		X	X	Following Informed Consent, patients will be required to complete their diaries daily beginning the day of their next cluster headache attack. Sites should review the diary compliance with the patient during specified office visits.

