Attachment 2. Protocol CGAM Clinical Laboratory Tests

Clinical Laboratory Tests

Hematology:	Clinical Chemistry:
Hemoglobin	Serum Concentrations of:
Hematocrit	Sodium
Erythrocyte count (RBC)	Potassium
Mean cell volume	Total bilirubin
Mean cell hemoglobin concentration	Direct bilirubin
Leukocytes (WBC)	Alkaline phosphatase
Neutrophils, segmented	Alanine aminotransferase (ALT)
Lymphocytes	Aspartate aminotransferase (AST)
Monocytes	Blood urea nitrogen (BUN)
Eosinophils	Creatinine
Basophils	Uric acid
Platelets	Calcium
HbA _{1c}	Glucose (fasting) ^a

Albumin
 Creatinine kinase (CK)
 Total cholesterol^a
 HDL^a

Urinalysis:

Specific gravity

pH

Protein

Glucose

Other

CCI [REDACTED]

PK Sample (LY2951742 serum concentration determination)

Immunogenicity

Urine Drug Screen^b

Ketones

Pregnancy Test (females only)^c

Blood

Serum pregnancy or FSH

Urine leukocyte esterase

Stored Samples

Plasma Storage (K+/EDTA CCI [REDACTED])

CCI [REDACTED]

RNA

Abbreviations: HDL = high-density lipoprotein; FSH = follicle stimulating hormone; HbA_{1c} = hemoglobin A1c ;

RBC = red blood cells; RNA = ribonucleic acid; WBC = white blood cells.

^a Fasting at Visits 3, 9, 13, 16, 22, 24 or early termination.

^b Performed at screening and may be repeated during the study at the discretion of the investigator.

^c Performed at screening per inclusion criteria number 8 and at Visits 22, 24 and ET.

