5.5.9.1.5. Laboratory Tests

The incidence rates of patients with treatment-emergent abnormal, high, or low laboratory values for each laboratory test based on Covance reference ranges at any time postbaseline will be summarized. The baseline and postbaseline definitions are summarized in [Table CGAM.5.3](#). The treatment comparisons will be assessed using Fisher's exact tests for SP III.

Patients will be defined as having a treatment-emergent low value if they have all normal or high values at baseline, followed by a value below the lower reference limit at any postbaseline visit. Patients with all normal or high values at baseline (no low values) will be included in the analysis of treatment-emergent low laboratory values. Patients will be defined as having a treatment-emergent high value if they have all normal or low values at baseline, followed by a value above the upper reference limit at any postbaseline visit. Patients with all normal or low values at baseline (no high values) will be included in the analysis of treatment-emergent high laboratory values.

For analytes simply classified as normal or abnormal, patients will be defined as having a treatment-emergent abnormal value if they have all normal values at baseline, followed by an abnormal value at any postbaseline visit. Patients with all normal values at baseline will be included in the analysis of treatment-emergent abnormal laboratory values.

The incidence of patients with the following elevations in hepatic laboratory tests at any time postbaseline will also be summarized, and comparison between treatment groups will be done for SP III using Fisher's exact test.

- The percentages of patients with an alanine aminotransferase (ALT) or aspartate aminotransferase (AST) measurement greater than or equal to 3 times (3 \times), 5 times (5 \times), and 10 times (10 \times) the Covance upper limit of normal (ULN) during the treatment period will be summarized for all patients with a postbaseline value.
- The percentages of patients with an alkaline phosphatase (ALP) greater than or equal to 2 times (2 \times) the Covance ULN during the treatment period will be summarized for all patients with a postbaseline value.
- The percentages of patients with a total bilirubin (TBIL) measurement greater than or equal to 2 times (2 \times) ULN during the treatment period will be summarized for all patients with a postbaseline value.

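### The treatment-emergent baseline for glucose, total cholesterol and HDL mixes a non-fasting Visit 1 draw with fasting later draws, which shrinks one safety table without favouring either arm

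*SAP*

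**What the plan says.** **Who enters the analysis.** For treatment-emergent abnormal laboratory values in SP III, SAP 5.5.1.6 (Table CGAM.5.3) admits "Patients in safety population with normal laboratory values at all nonmissing baseline visits (with respect to direction being analyzed") and sets the baseline at all of Visits 1 to 3. SAP 5.5.9.1.5 repeats the rule for the high direction: "Patients with all normal or low values at baseline (no high values) will be included in the analysis of treatment-emergent high laboratory values". One high value at any baseline visit is enough to exclude a patient.

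**How values are classified and compared.** SAP 5.5.9.1.5 summarizes incidence "for each laboratory test based on Covance reference ranges at any time postbaseline". For the randomized phase, "The treatment comparisons will be assessed using Fisher's exact tests for SP III". Neither section mentions fasting status.

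**Fasting state of the samples.** Protocol 7.1 says that at Visit 1 "non-fasting laboratory samples will be collected (fasting laboratory samples are collected at visits indicated in the study schedule"). The study schedule in Attachment 1 says "Except for V1, chemistry labs require fasting (no food or drink, except water, for at least 8 hrs"). Attachment 2 lists the analyte as "Glucose (fasting"). Its footnote a, attached to glucose, total cholesterol and HDL, reads "Fasting at Visits 3, 9, 13, 16, 22, 24 or early termination"; Visit 1 is not among those visits.

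**Other analyses of the same data.** The continuous laboratory analysis (Table CGAM.5.3 and SAP 5.5.9.2) takes the last non-missing value from Visits 1 to 3 as baseline. The categorical analyses in the GMB-treated population use Visits 1 to 3 for patients on galcanezumab in SP III and Visits 1 to 9 for SP III placebo patients, so Visit 1 counts there too.

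**The concern.** An all-visits baseline rule assumes that the baseline draws and the later draws measure the same quantity. For glucose they do not: one is taken without a fasting requirement and the others after at least 8 hours without food. A high value after a meal at screening is not evidence that the patient's fasting glucose was already high, yet the rule treats it so.

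At stake is the sensitivity of one prespecified randomized safety table. Patients can leave it because they ate before Visit 1, and a fasting abnormality that first appears on treatment is then missing from that table. The patients removed may also be more prone to high glucose than the rest, in which case more than a proportionate share of events is lost.

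**Working it through.** The documents give no glucose rate, no share of high Visit 1 values and no power for laboratory comparisons. There is therefore no stated figure to reproduce. The first step is reasoning from the text; the others are illustrations on labelled assumptions.

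**Step 1. Apply the rules to one patient.**

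| Visit | Fasting state (Protocol 7.1, Attachments 1 and 2) | Glucose (example) | Role in the treatment-emergent table |
|---|---|---|---|
| 1 | not fasting | high | baseline |
| 3, pre-dose | fasting | normal | baseline |
| 9 | fasting | high | post-baseline |

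Not all baseline values are free of a high, so the patient is outside the denominator and the Visit 9 high is not counted. In footnote a, Visit 9 is the only scheduled post-baseline fasting draw within SP III, so no later scheduled SP III draw restores the event. In the continuous analysis the same patient has the normal Visit 3 value as baseline, and the rise at Visit 9 is included.

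The exclusion needs a Visit 1 value above the upper reference limit. A post-meal value within the range excludes nobody.

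**Step 2. Denominator.** The planned minimum is 162 patients randomized 1:1 (SAP 5.2), and 162 / 2 = 81 per arm. Let f be the share of patients whose only high baseline glucose is the Visit 1 draw. Assume f between 5% and 25%.

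- 81 × 0.05 = 4.05, about 4 per arm, leaving 77.
- 81 × 0.25 = 20.25, about 20 per arm, leaving 61.

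**Step 3. Power of the planned test.** Exact power of the two-sided Fisher test at 0.05 is the sum, over all pairs of event counts with p ≤ 0.05, of the product of the two binomial probabilities. The incidences are assumed and are held fixed among the patients who remain.

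| f (assumed) | n per arm | 5% vs 20% | 5% vs 15% |
|---|---|---|---|
| 0 | 81 | 0.80 | 0.49 |
| 5% | 77 | 0.77 | 0.46 |
| 10% | 73 | 0.74 | 0.43 |
| 20% | 65 | 0.68 | 0.37 |
| 25% | 61 | 0.64 | 0.33 |

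**Step 4. If the excluded patients are at higher risk.** Let their on-study risk be r times that of the others. The share of events lost from the table is f·r / [(1 − f) + f·r].

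- f = 10%, r = 2: 0.20 / 1.10 = 18%. With r = 3: 0.30 / 1.20 = 25%.
- f = 20%, r = 2: 0.40 / 1.20 = 33%. With r = 3: 0.60 / 1.40 = 43%.

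The values of r are also assumptions.

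**The case against.** A reader might infer that the rule biases the comparison between arms, or that a glucose signal could go undetected in the trial. The documents support neither reading.

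- **Balance.** Visit 1 precedes randomization at Visit 3. Excluding patients on a Visit 1 value is a pre-randomization restriction applied alike to both arms, and the Fisher comparison remains valid among those who stay. This stands in full.
- **Other coverage.** SAP 5.5.9.2 compares change from baseline by ANCOVA, at scheduled visits and at endpoint, with a baseline that is normally the fasting Visit 3 draw. The excluded patients are in that analysis. HbA1c is drawn at screening and later, and does not depend on fasting state. This also stands: the loss is confined to the categorical table.
- **Different baselines by design.** For weight and temperature the SAP also uses the extreme of the baseline period for categorical changes and the last value for continuous ones. An all-visits rule avoids calling an abnormality new when it was seen before dosing, and a high Visit 1 glucose may carry some information about existing dysglycaemia. That justifies using several baseline visits. It does not justify mixing fasting states within one baseline.
- **Unknown laboratory handling.** The laboratory may report Visit 1 glucose as a separate test or against a non-fasting range. If so, the problem shrinks or disappears. Neither document says so.
- **Scope.** The 5% to 25% share has no source in the documents. In practice this is mainly about glucose, since cholesterol and HDL are probably affected less. Laboratory values are not among the comparative safety objectives listed. All of this limits priority.

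**Conclusion.** The point holds in a narrow form. As written, the categorical treatment-emergent baseline for the footnote-a analytes combines a non-fasting draw with fasting ones. A patient whose only high value is the non-fasting one is excluded, and a new fasting high is left out of that table. The consequence is a smaller denominator and lower sensitivity in one table; no directional bias is expected, and assessment of glycaemia elsewhere in the plan is not lost.

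The size is unknown. On an assumed 5% to 25% share, about 4 to 20 of 81 patients per arm drop out, and power for an assumed 5% versus 20% incidence falls from 0.80 to between 0.77 and 0.64. If those excluded carry two to three times the risk of the others, the share of events missing from the table exceeds the share of patients missing. All of this rests on Visit 1 glucose being classified against the same range as the later values, which the documents neither confirm nor deny.

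**What to change.** Low priority. In Table CGAM.5.3 and SAP 5.5.9.1.5, state that for the analytes carrying footnote a of Protocol Attachment 2 (glucose, total cholesterol, HDL) the treatment-emergent baseline uses fasting pre-dose samples only:

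- Visit 3 for SP III, and for patients on galcanezumab in SP III in the GMB-treated analyses;
- Visits 3 and 9, before open-label dosing, for SP III placebo patients in the GMB-treated analyses.

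Keep all of Visits 1 to 3 (or 1 to 9) for every other analyte. If the laboratory already reports Visit 1 glucose as a separate non-fasting test, a sentence saying so would suffice for glucose.

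The cost is one SAP sentence and a programming filter, with no new samples. There are two downsides: a patient without a fasting Visit 3 result is not evaluable for these three analytes in SP III, and baseline rests on fewer draws, so a single normal Visit 3 value carries more weight.
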